8.8.2 Site Audits and Inspections

Not applicable.

8.8.3 Safeguards, Security and Traceability of Contacts

Operators of the call centres specialized in health surveys will be assigned to the project and trained on the survey methodology prior to fieldwork. The email contacts and phone calls will be traced using management software.

Participating HCPs/patients/carers will access the website (<https://> secured site) via a secure link. This link is unique to each HCP/patient/carers.

The answers provided will be collected in an anonymous way, and only aggregated data presented as a synthesis will be transmitted to the MAH.

Data will be recorded in a central database and tracked using an audit trail. The system will enable retrieving all introduced data at any time and will include security elements to

prevent anyone other than authorized staff from accessing data. Each user will have a specific profile which will limit his/her use of the database. A copy of the database and the application files will be made outside the server housing the web-based study. These copies for security purposes will be periodically made and stored outside this server.

8.8.4 Retention of Records

The study documentation will be stored in the study master file.

The data from the online questionnaires and the phone interviews will be stored on the study database for 5 years.

Data storage will be in line with national data protection requirements for each of the countries where the study will be conducted.

All documentation pertaining to the study, including electronic records will be retained for a minimum of 5 years after the end of the study.

8.9 LIMITATIONS OF THE RESEARCH METHOD

Bias

The potential for selection bias of physicians participating in a survey is an inherent bias/limitation to any study based on volunteer participation. For instance, it is possible that HCPs willing to participate in the study are those with the highest awareness of the risks associated with Hemlibra®. In order to quantify any selection bias, the distribution of each stratification criterion of physicians (country, speciality, and the other available characteristics present in the screening log) will be compared between participants and non-participants.

Additionally, non-response bias may also be introduced into the study if targeted HCPs have activated filters in their mailbox that block spam and unsolicited emails. Having multiple email addresses could also affect responsiveness, especially if the one used for sending the invitation is not the primary address. HCPs who do not check their email frequently might not receive the invitation during the recruitment period. These are among the reasons why the HCPs will also be contacted by phone.

Moreover, online surveys may promote information bias that may result from social desirability, which refers to the tendency of physicians to give socially desirable/expected responses instead of choosing those reflecting their current knowledge or behaviour, e.g. physicians can copy-paste or refer to information gathered online instead of giving their own opinions ([Wyatt 2000](#)).

Social desirability can affect the validity of survey research findings, but the use of pre-populated items in the questionnaire could/tends to reduce this bias ([Nederhof 1985](#)).

Theoretically, the social desirability bias may also arise when the patients are recruited by the same HCP who has participated in the survey. There is also a potential for a HCP who participated in the survey to increase the awareness of his or her patients about the topic covered in the survey. However, due to the anonymity of the survey, the competitive recruitment (the HCP will not be certain if a patient questionnaire will ultimately be considered in the study), and the fact that the results of the patient survey will not be analysed per centre but as separate samples, this limitation is less likely to happen. As a result, we do not consider it necessary to distinguish between HCPs who participate in the survey from those who recruit patients.

The access to the online questionnaire interface will be limited to the invited participants. Each participant will receive a unique link (URL) to the questionnaire and will only be allowed to participate once.

This survey includes products that are prescribed to patients under 18 years of age. In such cases, the questionnaire will be filled by the parent or the guardian, which may impact responses to questions related to awareness and knowledge of Hemlibra® risks.

Finally, the patient recruitment model, which is done exclusively through HCPs, can introduce a potential bias if the HCPs select patients in a non-random manner.

Limits inherent to surveys

In such surveys, the generalisation and external validity of the results is restricted to HCPs who have an active email address and willing (and able) to answer a questionnaire online. These physicians may not be fully representative of the whole targeted population ([Wyatt 2000](#)).

In terms of the patient survey, the use of the online questionnaire format limits participants to patients with internet access.

Generalisation of the survey results to the overall target population with adjustment

The most important limitation for the generalization of the results are the sample size which could yield a confidence interval which is very wide. Although all reasonable efforts will be undertaken to achieve the required sample size, if the final sample is below 30, the usual statistical tests will be of limited validity and the generalization of the sample will be jeopardized.

The raw survey results can only be generalized to the overall target population, except if a sample adjustment is applied. For more transparency and accuracy, both unweighted (i.e., raw data) and weighted results will be presented.

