HCPs will be asked to distribute up to 18 survey kits to their patients or carers. Assuming 15-20% of HCPs agree to distribute the survey and that 20-40% of patients/carers respond, our target sample size is 70 patient questionnaires, including 25-35 from patients with inhibitors or their carers.

Data Analysis

The statistical analysis will be conducted using the SAS software V9.4 on Windows™ (SAS Institute, North Carolina, USA).

Results will be presented, overall and by geographic region. *Other criteria for grouping may also be used for results presentation e.g., Euro Health Consumer Index.* Continuous variables will be described by the number of valid cases and missing data (if applicable), mean, standard deviation, median, first quantile (Q1), third quantile (Q3), minimum, and maximum. No missing data will be imputed. Categorical variables will be described as the total number and relative percentage per category. Confidence intervals of 95% will be estimated when relevant.

Individual awareness, knowledge, and adherence values will be calculated as the percentage of correctly answered survey questions; values will range from 0 to 100% with 100% representing the percentage of all knowledge questions and behaviour questions being answered correctly, respectively.

Analysis will be done on questions common to all HCPs and patients/carers as well as on a limited number of questions presented to the subgroup of patients with concomitant use of aPCC (FEIBA) and Hemlibra® (or their carers).

Potential selection bias will be assessed by comparing the distributions of available characteristics (e.g. region, type of practice and speciality) between respondent and non-respondent HCPs, if applicable and feasible.

Success on the educational materials for additional risk minimisation measures will be defined a priori as achieving overall scores of $\geq 75\%$ for awareness and adherence and $\geq 60\%$ for knowledge for HCPs and $\geq 60\%$ in all areas for patients/carers. Overall success is defined as success on all three measures for both HCPs and patients/carers (see Section 8.7).

The planned analyses will be fully described in the Statistical Analysis Plan (SAP) to be developed after protocol approval by the European Medicines Agency (EMA).

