 - HCPs can also choose to participate in the survey by phone in the local language. In this case, an appointment for a phone interview will be scheduled with them.
- Screening questions included at the start of the questionnaire include that HCPs must have prescribed Hemlibra® at least once prior to the study and are not employed by Roche or IQVIA
- Once HCPs have passed the screening questions of the questionnaire, they are moved through the questions one question at a time. For the web-based questionnaire, HCPs can only progress to the next question when the previous question was answered, and only wholly completed questionnaires can be

submitted. If a phone interview is requested, the interviewer will complete the online questionnaire with the HCP.

- If the questionnaire is not completed within one week, the HCPs will be sent a reminder by email one week after the link was sent to them
- If the study sample size is not achieved in the country, a second reminder by phone will be conducted 1.5 weeks after the link has been sent.
- If the questionnaire is still not fully completed, a third and final reminder will be sent to the HCPs by email approximately three weeks after the start of the questionnaire.

For each HCP of the sample, the number of contacts and the date and time when he/she completed the online questionnaire will be recorded. An HCP will be considered as unreachable if he/she has been contacted between 3 and 5 times without having received any answer.

The recruitment in each country will be stopped when the target is reached. If the HCP list has been exhausted in any particular country, the recruitment in this country will be prematurely ended and a strategy will be determined to adjust the sample size with associated weighting.

Patients

HCPs that agree to participate in the patient survey will be sent informational material (kits) for distribution to up to 18 of their patients. The kit will include an explanation of the study and a simplified guide for taking the online questionnaire.

A pre-printed random unique number on the kit is registered by the HCP on a tracking web site. Tracking kit numbers allows monitoring of the number of patient questionnaires coming from the same practice. No log would be kept at the physician level which would link the kit number and the patient's identity.

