8.7.4 Questionnaire Analysis

Analysable questionnaires are those completed and submitted by the participants on the web. If the questionnaire is just filled on the web but not submitted, the questionnaire will not be analysed and will be discarded.

Analysis will be done on questions common to all HCPs and patients/carers as well as on a limited number of questions presented to the subgroup of patients with concomitant use of aPCC and Hemlibra® (or their carers).

For each question, the number and percentage of participants correctly answering each question will be presented. Individual awareness, knowledge, and adherence values will be calculated as the percentage of correctly answered questions; values will range from 0 to 100% with 100% representing the percentage of all questions in the category being answered correctly.

Awareness questions

- HCP questionnaire: Q8 and Q9
- Patient/carer questionnaire: Q1 and Q2

Knowledge questions

- HCP questionnaire: Q10, Q11, and Q12
- Patient/carer questionnaire
 - All: Q3, Q4, Q5, and Q6

Adherence questions

- HCP questionnaire: Q13, Q14, Q15, Q16, and Q17
- Patient/carer questionnaire
 - All: Q11
 - Additional questions for patients (or their carers) taking aPCC and Hemlibra: Q8, Q9, and Q10

In a first step, calculations will be performed on raw data. No projection factor will be applied to generalize the results to the entire prescribers' universe. As a consequence, the line "Overall - unweighted results" will show only the results observed on the overall sample and will not reflect the geographies' universe since this sample is not proportional to the size of the lists in each geography.

If possible, in a second step, the results will be weighted according to the real proportion of HCPs or patients/carers in a geographical region in order to accurately reflect the population that the survey seeks to measure.

Possible *participation* bias will be assessed by comparing the distributions of available characteristics (e.g., geography, type of setting [e.g., haemophilia treatment centre or HCCC], and speciality, if applicable and feasible) between respondents and non-respondents.

Assessment of success

The proportions of correct and appropriate answers to selected questions asked in the questionnaire will be presented for HCPs or patients/carers who provided answers to those questions, as outlined below.

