8.10 OTHER ASPECTS

Strengths of the research methods

1. The information contained in the OneKey list of each country is updated continuously with proactive updates. Quality controls are performed on OneKey content on a regular basis. OneKey is the most comprehensive list of HCPs in the world with very high coverage in most countries.
2. The sampling of HCPs follows a randomized method which guarantees the representativeness of the contacted population in order to limit selection bias due to voluntary participation. Batches of HCPs will be contacted up to five times before moving forward to other HCPs in the lists.
3. The questionnaire includes general questions followed by specific ones in order to limit a learning process during the survey. As the physicians may understand the right answer in subsequent questions, it would not be possible to go back in the questionnaire and edit answers in former questions.
4. The questionnaire is tested for its clarity. It is also checked whether there are questions which would suggest a specific answer for any reason for example social desirability. The translation of the questionnaire is tested before implementation.

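### Section 8.9 promises to quantify selection bias by comparing background characteristics, which cannot measure self-selection on awareness, knowledge or adherence

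*Protocol*

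**What the plan says.** Section 8.9 (Bias) treats volunteer selection as inherent to this kind of survey and names a mechanism: "it is possible that HCPs willing to participate in the study are those with the highest awareness of the risks associated with Hemlibra". The next sentence gives the remedy: "In order to quantify any selection bias, the distribution of each stratification criterion of physicians", the criteria being "country, speciality, and the other available characteristics present in the screening log) will be compared between participants and non-participants".

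The same kind of check appears twice more in softer terms. The synopsis says "Potential selection bias will be assessed by comparing the distributions of available characteristics (e.g. region, type of practice and speciality" and so on. Section 8.7.4 says that possible participation "bias will be assessed by comparing the distributions of available characteristics", naming geography, setting and speciality, where applicable and feasible.

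Section 8.10 lists as a strength that random sampling of HCPs "guarantees the representativeness of the contacted population in order to limit selection bias due to voluntary participation".

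Section 8.4.2 states that for each sampled HCP "the number of contacts and the date and time when he/she completed the online questionnaire will be recorded". The uses that the protocol gives for contact information are operational: reminders, tracing of contacts, and classing an HCP as unreachable after 3 to 5 unanswered contacts.

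The HCP success thresholds in 8.7.4 are 75% for awareness, 60% for knowledge and 75% for adherence. The objectives in 7.2 refer these proportions to targeted prescribers.

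**The concern.** The bias named in 8.9 works through awareness, which is itself an outcome. The planned comparison contains no outcome, so it cannot return an estimate of that bias. Respondents and non-respondents may have identical distributions of country, speciality and setting and still differ in what they know and do.

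Weighting does not fill the gap. Sections 8.5.3, 8.7.2 and 8.7.4 reweight to the real proportions by region or country, with speciality also mentioned. That corrects the mix across strata and leaves self-selection within a stratum untouched.

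The sentence in 8.10 has a related fault. A random draw makes the contacted sample representative of the list. It has no bearing on which of those contacted choose to answer, and 8.9 itself calls that bias inherent to volunteer participation.

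At stake is how the success verdict is read. If the report presents a balanced table under a heading of quantified selection bias, it claims more than the method delivers, and the thresholds may be taken as met for targeted prescribers when they are shown only for those who replied.

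**Working it through.** **The plan's own figures.** Section 8.5.1 uses n = P(1−P)Z²/e² with P = 0.5 and Z = 1.96.
- e = 0.15: 0.25 × 1.96² / 0.15² = 42.7, so 43 as stated.
- Half-width at the target of 40: 1.96 × √(0.25/40) = 15.5 points, in line with the stated approximate 15%.
- Half-width at the 107 HCP questionnaires reported in the amendment rationale: 1.96 × √(0.25/107) = 9.5 points.
- Invitations: 400 × 10% = 40, as stated.

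These figures reproduce. They describe sampling error only and say nothing about who replies.

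**Can the planned check see the named bias?** Let p be true awareness and k the ratio of response rates, aware to unaware. The documents do not give k; it is an assumption. Observed awareness is pk / (pk + 1 − p).
- With p = 0.60 and k = 2: 1.20 / (1.20 + 0.40) = 75%, which is the awareness threshold.
- At 10% overall response, the unaware reply at 0.10 / 1.60 = 6.25% and the aware at 12.5%.

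If the same k applies in every country and speciality, and awareness does not differ between them, the distributions of participants and non-participants on those items are identical. The comparison shows nothing while the result is 15 points too high.

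Solving for the true value, p = T / (T + k(1−T)), when the observed value sits exactly on the threshold T:

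| k (assumed) | True value, T = 75% | True value, T = 60% |
|---|---|---|
| 1 | 75.0% | 60.0% |
| 1.25 | 70.6% | 54.5% |
| 1.5 | 66.7% | 50.0% |
| 2 | 60.0% | 42.9% |
| 3 | 50.0% | 33.3% |

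**What non-respondents do to the verdict.** Population value = r × 0.80 + (1 − r) × (0.80 − d), with r the response rate, 80% among respondents assumed, and non-respondents d points lower (assumed).

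| d | r = 10% | r = 30% |
|---|---|---|
| 5 points | 0.080 + 0.675 = 75.5% | 0.240 + 0.525 = 76.5% |
| 10 points | 0.080 + 0.630 = 71.0% | 0.240 + 0.490 = 73.0% |
| 15 points | 0.080 + 0.585 = 66.5% | 0.240 + 0.455 = 69.5% |

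Break-even among non-respondents for 75%: (0.75 − 0.08) / 0.90 = 74.4% at r = 10%, and (0.75 − 0.24) / 0.70 = 72.9% at r = 30%. The 10% is the lowest rate that 8.5.1 allows for; the 30% is an assumption.

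**How much a table by contact number or timing could show.** For an assumed split of 85% in early and 65% in late responders, power is about 30% with 20 per group (n = 40 halved) and about 67% with 53 per group (n = 107 halved). Three contact groups within three regions would make nine cells, about 107 / 9 = 12 HCPs each if evenly spread, with a half-width of 1.96 × √(0.25/12) = 28 points. The table is therefore usable overall, as description, and too sparse within region.

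**The case against.** **The bias is disclosed.** Section 8.9 names self-selection, limits generalisation to HCPs willing and able to answer online, and says they may not represent the whole target population. Section 8.7.4 calls the thresholds subjective and promises to put results in context. The synopsis and 8.7.4 say only that potential or possible bias will be assessed. This stands: the fault is in the claim to quantify in 8.9 and the claim in 8.10, not in silence about the problem.

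**Details belong to the SAP.** Section 8.7 defers detail to a SAP that is not at hand, and results by contact number could be in it. This also stands, so their absence here is not in itself the defect. A SAP table would not correct what 8.9 and 8.10 assert.

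**The plan can see part of the bias.** Section 8.7.4 profiles HCPs with incorrect answers by geography, speciality, duration of practice and setting, and compares trial investigators with routine prescribers. Read beside the participation comparison, this can show whether a characteristic linked to poor results is under-represented. Self-selection within such groups stays invisible. A reader might infer that inflation of any kind must go undetected; the documents do not support that.

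**Contact counts are used.** A reader might infer that they are recorded for nothing. In fact 8.4.2 uses contacts to class an HCP as unreachable, a category that 8.7.3 separates out, and 8.10 describes up to five contacts before moving on, which does address non-reply. What is absent from the protocol is any link between contacts or timing and the answers.

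**Late responders are a poor stand-in.** The phone reminder is sent only where a country has not reached its sample, and 8.9 attributes some non-reply to mail filters and secondary addresses. Setting non-respondents equal to the last-contact group and restating the verdict would therefore be noisy and confounded with country. This is accepted, and the fix does not do it.

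**Answers are anonymous.** Identifying details are stored apart and only aggregates reach the sponsor. The survey operator can still carry a contact count or completion date without an identity.

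**Conclusion.** The point holds as a mismatch between a stated purpose and a stated method. Comparing country, speciality and screening-log items describes differences in observed characteristics; it does not quantify self-selection on awareness, knowledge or adherence. Random contact does not limit who chooses to reply. Neither conclusion depends on what the SAP contains.

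The size is illustrative. The 80%, the gaps d and the ratio k are assumptions. Under them a gap of 5 points still meets 75%, while gaps of 10 or 15 points do not, at 10% or 30% response. A reader might infer that the HCP awareness verdict would fail in the target population. The documents do not support that: they give no respondent result and no gap. The 10% is a lower planning figure among invited haematologists, all of whom could have prescribed Hemlibra but some of whom never did. Section 8.7.3 removes only those confirmed ineligible, so silent never-prescribers stay among the non-respondents although they lie outside the target population. To that extent the weight given to non-respondents above is too large.

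**What to change.** 1. In 8.9, replace the claim in "In order to quantify any selection bias, the distribution of each stratification criterion of physicians" with wording that the comparison describes differences in observed characteristics between participants and non-participants and cannot exclude self-selection on the outcomes.
2. In 8.10, confine "guarantees the representativeness of the contacted population in order to limit selection bias due to voluntary participation" to its first half: keep representativeness of the contacted sample and remove the part about limiting bias from voluntary participation.
3. In 8.7.4, add a descriptive table of the three HCP domain results by number of contacts, or by early versus late completion, from the data recorded under 8.4.2. Present it overall rather than within region. State that late responders are an imperfect proxy for non-respondents, that phone reminders depend on recruitment in the country, and that groups are small.
4. In 8.7.4, add a sensitivity display showing whether each HCP threshold is still met over a range of assumed values for eligible non-respondents. Because the share of silent HCPs who ever prescribed is unknown, vary the response rate among eligible HCPs as well.

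The cost is two edits to the text, one table and one calculation. The operator must carry the contact count or completion date into the analysis file; no new question to HCPs is needed. The downside is limited precision, so neither output should be read as a measurement of the bias.
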